9.4 Recruitment for 6-month extension

All mother-infant pairs who are currently being followed up for the first 6 months of their infants' lives are eligible to take part in this study and will be approached for re-consent to an additional 6 months of follow-up at or before the 6-month visit. Mothers and infants will not be screened but rather all current participants will be approached and asked to re-consent for continued follow-up in the study. Study staff will read the recruitment script before asking the participant for consent.

9.5 Replacement of infants who die in the first 72 hours

As described in the exclusion criteria for the prospective cohort, it will not be possible to identify all infants with severe or critical illness before discharge. Because not all diagnoses can be made definitively before discharge, some critically ill infants may end up in the prospective cohort, and may, unfortunately, die early.

These cases will not contribute much data to the study on their growth and feeding patterns, and may erode our ability to achieve our target sample size. We aim for 350 mothers at enrollment with 300 still

enrolled at 6 months. The drop of 50 mothers is due to expected loss to follow up as well as deaths. However, this margin may not be large enough to cover all the deaths if we include infants who have serious illnesses that are not apparent at discharge. In that case, we may end up with more infants than expected dying in the first few days, and fewer than 300 infants by six months.

For these reasons, we will consider an enrolled infant who dies within the first 72 hours to be excluded from the cohort, and we will recruit an additional infant in its place. In effect, this puts an additional inclusion criterion on this cohort, which is surviving the first 72 hours of life. If the infant dies at any time after 72 hours, he or she will not be replaced in the sample.

Baseline data from infants who die in the first 72 hours will not be included in the formal analyses, but may be included in post-hoc explorations.

9.6 Assessment of congenital abnormalities and serious illnesses in infants

Some of the congenital abnormalities and serious illnesses will be readily apparent at birth, such as cleft lip. However, at first screening, it may not be possible for the clinicians to conclusively state whether the infant has some of the other congenital abnormalities or serious illnesses in our exclusion criteria. Some conditions may take a day or several days to fully develop.

[figure not shown]
Figure 2 shows how cases will be handled. Infants who clearly have the condition or illness at the first screening will be ineligible, and if they clearly do not, they will be eligible. In the event that it is unclear, then the study staff will revisit the mother-infant pair several hours later, the amount of time depending on the clinical judgment of the facility staff. If at that repeat screening the infant's condition is still not clear, study staff will again delay screening and revisit later.

In the end, the final screening will take place when the infant is discharged or when 72 hours has elapsed since birth, whichever comes first. In either case, as shown in Figure 3, if the condition is still unclear, then the infant will be treated as eligible. If the infant is enrolled at discharge before 72 hours, and then happens to die within the 72 hour mark, that infant will be replaced in the prospective sample. If the infant is enrolled at 72 hours, it will be kept in the prospective sample even if it dies soon afterward.

Figure 2. Screening for infant conditions

Screening for infant conditions

Congenital conditions that interfere with feeding
Critical or serious illnesses that jeopardize survival to 72 hours

9.7 Overlap between observation and prospective cohort recruitment

There is no requirement for women in the observation group to participate in the prospective cohort, or vice versa. The consents are entirely separate. If a woman is approached for the observation and declines to participate, she may still be approached later for the prospective cohort.

9.8 Informed consent

The goal is to follow LBW infants for up to 12 months, with a regular schedule of visits to collect both survey and anthropometric data, review of medical chart, including HIV status, for visits occurring at the study facility, as well as observation of feeding when relevant. We will use a full informed consent process, involving a description of the study, discussion of risks and benefits, ability to withdraw at any time, and other required information. This consent will be documented with the woman's signature. All women will receive a copy of the consent documentation.

In the case of illiteracy, we will use a thumbprint for the woman's signature, with an additional signature from an impartial witness to the consent process.

In the case that a mother consents to participate but asks a surrogate to answer questions for her, the action required will be country-specific in alignment with site requirements:

- Tanzania: Mother will complete and sign an additional "caretaker consent form", authorizing a surrogate to share information about her.
- India: Mother's signed consent is sufficient; no further action required.

- Malawi: Only allowed in the case that the mother is in the ICU and unable to answer: the trusted guardian will sign a separate consent form (same version as mother's consent form)

If a mother dies during the study period, we will ask permission from the family to continue following the infant. A new informed consent process will be conducted with the infant's primary caregiver.

6-month extension: Study staff will ask the mother to reconsent around before their 6-month study visit as part of their original follow-up in the LIFE study. The recruitment script will be read before reviewing the consent form. The study staff will give the participant time to review, ask questions and think about whether or not they would like to consent to their participation.

9.9 Incentives

Women in the prospective cohort and extension may be asked to come to the facility when they otherwise would not. They will be provided a standard travel allowance for each visit that they make to the facility for a study visit, in alignment with local site and ethics review board requirements.

6-month extension:

(Insert site specific location: Tanzania and or Malawi): For the follow up phone calls at around 7.5 and 10.5 months: Participants will not incur any costs associated with receiving the phone calls. As such, there will be no compensation to participants for phone calls during these time points.

9.10 Benefits to participation

The benefits to study participants may include additional monitoring of a child's growth and earlier referral to care as part of participation in the cohort study.

9.11 Maternal or infant death during study period

In the case of a maternal death during the study period, we will ask permission from the family to continue following the infant. A new informed consent process will be conducted with the infant's primary caregiver.

[figure not shown]
In the case of an infant death during the study period, we will not continue to collect study information on the mother; however, we will ensure that the mother is receiving adequate care, through appropriate referral mechanisms.

Verbal autopsies of the infant would be desirable, but they were not budgeted for as part of this study. In Tanzania, the study team will have to perform a verbal autopsy at 40 days post-death to meet government regulations, so they will be available for that site. If possible, we will gather information from verbal autopsies.

9.12 Sample size

The sample size will be as large as possible given constraints in time, recruitment rates, and budget. We do not plan to do any hypothesis testing using this observational data. The main statistical results will be point estimates and confidence intervals for certain rates, such as the percent of LBW infants who do not successfully breastfeed, require tube feeding, or the percent who develop certain conditions. The final sample size will determine the precision of the estimate, as shown in Figure 3. For example, with a sample of 250 infants, a true proportion of 5% can be estimated with precision of +/- 2.7%. The 95% confidence interval would be 2.3% to 7.7%.

Figure 3: Margin of error in estimation of a single proportion with a single sample

While we would like the precision of our estimates to be as high as possible, we have no statistical requirement for a particular number. Instead, we propose aiming for 350 enrolled mothers at each site, with an estimated final sample of 300 mothers in each site due to loss to follow up and withdrawal. This target will give a reasonable level of precision on the point estimates and appears logically achievable in the study period.

The sample of mothers will be different from that of infants due to multiple births; thus we expect up to 850 individuals be enrolled in the study if there are many sets of twins. We do expect twins to occur with some frequency in our samples, since we are selecting for LBW infants, and many multiples are LBW. The overall rates of multiple births in the general population are 7.2 per 1,000 births in India, 20.8 in Malawi, and 18.8 in Tanzania (Smits and Monden, 2011). We expect higher rates of multiples in our study population, so to be conservative, we double these estimates and assume our sample will include 14.4 multiples per 1,000 births in India, 41.6 in Malawi, and 37.6 in Tanzania. If these rates hold, and assuming both twins are eligible and enroll, then our sample of 300 women would include 304 infants in India, 313 infants in Malawi, and 311 infants in Tanzania. This will not greatly change the precision of the estimates shown for a sample of 300 in Figure 3.

The presence of twins will also introduce an element of clustering, since the outcomes within a set of twins may be highly correlated. The clustering will make the confidence intervals larger, with the degree of enlargement depending on two factors: 1) how many sets of twins are both enrolled in our sample, and 2) how correlated the outcomes are within twins (intraclass correlation coefficient, or ICC). This degree of enlargement can be expressed as the design effect (DEFF), or the increase in the sample size that is required to detect the same difference at the same level of statistical power, given the clustering in the sample.

Other research using large samples of births that include some proportion of multiples (Yellin et al, 2017) shows that the DEFF can be calculated as:

$$DEFF = 1 + \rho \gamma_p$$

where ρ (rho)= ICC of the outcome within twins, and γ_p (gamma) is the proportion of the total sample of infants who are twins. This proportion is defined as:

N = total number of infants in sample (as opposed to the total sample of mothers)

M_S = total number of singletons in sample

[figure not shown]
M_P = total number of pairs of twins in sample

$\gamma_p = 2M_P / N$

To estimate the DEFF for this study, we draw ICC estimates from the literature. A review of birth outcomes research (Yellin et al, 2018) presents ICCs for twins for three outcomes of interest to LIFE: 0.26 and 0.85 for admission to the NICU; 0.25 and 0.36 for any sepsis; and 0.08 and 0.17 for proven necrotising enterocolitis. We may not be able to predict the ICCs we observe in the LIFE sample from these because these estimates show such a wide range, and were drawn from developed settings.

Because we may not be able to predict the ICCs in LIFE, we estimated DEFF for each study country at ICCs ranging from 0.1 to 0.8 (Figure 4). India's DEFFs will likely be lower than the other sites' because its baseline twinning rate is lower. In the most extreme case of ICCs in the 0.8 range, the largest DEFFs we would expect in this study would be about 1.06, or a 6% increase in sample size needed for the same precision at the same level of power. In a sample of 312 infants given a DEFF of 1.06, the precision of the point estimate would be as though we had a sample of 294 (312/1.06). This will not introduce a large distortion to the precision estimates.

Figure 4: Estimated design effects at a range of ICCs, by study country

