9.20 Data analysis

As most of the quantitative data collected is being used for descriptive epidemiology of LBW infants, we will use means, medians and standard deviations to describe continuous variables. Categorical variables

will be analyzed with frequencies and proportions, as appropriate. Confidence intervals around all measures will be constructed to take any clustering into account.

For anthropometric analyses, we will use the INTERGROWTH charts to describe growth velocity and trajectories for the infants, including stunting (length-for-age z-score, LAZ), underweight (weight-for-age z-score, WAZ), and wasting (weight-for-length z-score, WLZ). To determine Z-scores, we will use the INTERGROWTH-21st standards for preterm infants (<37 weeks gestation), and the WHO postnatal growth standards for term infants (>37 weeks gestation) (Villar et al 2015).

Where possible, we will relate these anthropometric measures with reported infant feeding, using correlations for continuous variables or cross-tabulations of categorical variables. Any further analyses will be post-hoc and described separately.

6-month extension:

As with the original LIFE study, we will utilize mixed methods to fully understand the growth trajectories and care for LBW infants during the first 12 months of life. We will use the full cohort from 0 to 12 months of age to assess growth trajectories and velocities over time, evaluating the impact of complementary feeding (food types and timing) on infant anthropometrics, and assessing morbidities over time.

We will use descriptive methods for initial description of the LBW cohort with means, medians and standard deviations for continuous variables. Categorical variables will be analyzed with frequencies and proportions, as appropriate. Confidence intervals around all measures will be constructed to take any clustering into account.

For anthropometric analyses, for preterm infants we will use the INTERGROWTH-21st postnatal growth standards for preterm infants to describe growth velocity and trajectories for the infants up to 12 months of age, including stunting (length-for-age z-score, LAZ), underweight (weight-for-age z-score, WAZ), and wasting (weight-for-length z-score, WLZ). To determine Z-scores, we will use the INTERGROWTH-21st standards for preterm infants (<37 weeks gestation), and the WHO postnatal growth standards for term infants (>37 weeks gestation).

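### Cumulative percentages are planned as simple proportions with no denominator and no rule for death or loss, at 14% expected attrition that includes deaths

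*Combined protocol and SAP*

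**What the plan says.** On the type of result, section 9.12 states: "The main statistical results will be point estimates and confidence intervals for certain rates". Its examples are cumulative: unsuccessful breastfeeding, need for tube feeding, and development of certain conditions.

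On size, 9.12 sets the enrolment target: "we propose aiming for 350 enrolled mothers at each site". The number expected to remain is lower, and the plan describes it so: "with an estimated final sample of 300 mothers in each site due to loss to follow up and withdrawal". It makes precision depend on the final sample size, and after adding twins it concludes: "This will not greatly change the precision of the estimates shown for a sample of 300 in Figure 3".

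Section 9.5 describes the 300 as the mothers still enrolled at 6 months and gives a different reason for the difference: "The drop of 50 mothers is due to expected loss to follow up as well as deaths". So 9.12 lists loss and withdrawal, and 9.5 lists loss and deaths. Neither splits the 50.

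On analysis, section 9.20 says: "Categorical variables will be analyzed with frequencies and proportions, as appropriate". It adds confidence intervals that allow for clustering. It does not name the denominator, say how a death enters a percentage, or say how an infant with partial follow-up is counted.

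**The concern.** At 6 or 12 months, whether an infant ever had a condition is fully known only for infants followed that long. The others either died or were lost, and these need different treatment. An infant who died has a complete history, and any condition recorded before death is a real event. An infant lost at week 2 has an unknown later history.

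A simple proportion forces a choice. Taken over those remaining, it drops infants who had the condition and died. Taken over all enrolled, it assumes that infants lost early never had the condition. Section 9.20 makes neither choice, so it could be made after the data are seen, and differently at each site.

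Objective 2 is to document morbidity and lack of success on mother's own milk, and section 9.18.6 lists sepsis, necrotising enterocolitis, pneumonia and hospitalisation. These are plausibly linked to death, although the documents give no figures. Section 2.1 has sites analysed separately, so differences in mortality or retention could shift each site's figures by a different amount. The re-consent step in section 9.4 adds a further route out before the 12-month results.

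**Working it through.** **Plan's own figure.** Section 9.12 says "with a sample of 250 infants, a true proportion of 5% can be estimated with precision of +/- 2.7" percent, and "The 95% confidence interval would be 2.3% to 7.7" percent. The Wald half-width is 1.96 × √(p(1−p)/n). With p = 0.05 and n = 250 it is 2.70 points, or 2.3% to 7.7%, so the figure reproduces. At p = 5% the half-width is 2.47 points for n = 300 and 2.28 for n = 350. Sizing on 300 is therefore slightly conservative and is not itself a source of bias.

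**Inputs from the documents.** 350 enrolled, 300 final, drop 50/350 = 14.3%. These count mothers; twins raise the infant count slightly (304 to 313 per 300 mothers in 9.12), which is ignored here.

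**Inputs assumed, because the documents give none.** d = 10, 20 or 30 of the 50 are deaths after 72 hours. A share r = 40, 60 or 80% of those infants had the condition. Completers and infants lost alive both have it at 10%.

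**Denominator 1: those remaining.** The completer estimate is 10%. The percentage among all enrolled is (0.10 × (350 − d) + r × d)/350:

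| Deaths d | r = 40% | r = 60% | r = 80% |
|---|---|---|---|
| 10 | 10.9% | 11.4% | 12.0% |
| 20 | 11.7% | 12.9% | 14.0% |
| 30 | 12.6% | 14.3% | 16.0% |

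The margin at 10% and n = 300 is 1.96 × √(0.1 × 0.9/300) = 3.4 points. The gap exceeds it in three of the nine cells: 4.0 points (d = 20, r = 80%), 4.3 (d = 30, r = 60%) and 6.0 (d = 30, r = 80%). In those cells the share of affected infants who die is 16/49 = 33%, 18/50 = 36% and 24/56 = 43%.

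**Direction.** Let p be the true risk and f the share of affected infants who die. With other losses at random, the expected percentage among those remaining is p(1 − f)/(1 − d/350). It lies below p only when f > d/350, which is 2.9% for 10 deaths and 8.6% for 30. For p = 5% and d = 10 to 30:

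- f = 0: 5.1 to 5.5% (slight over-count)
- f = 10%: 4.6 to 4.9%
- f = 20%: 4.1 to 4.4%
- f = 50%: 2.6 to 2.7%

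**Denominator 2: all enrolled.** If 20 to 40 of the 350 are lost before any event and counted as event-free (assumed), a true 10% reads as 10% × 330/350 = 9.4% down to 10% × 310/350 = 8.9%.

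**The case against.** A reader might infer that the plan will under-count conditions that kill infants. The documents do not support that.

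- The 300 is a planning size. No section limits the percentages to those still enrolled at 6 months, and the 9.12 sentence about the drop does not mention deaths.
- Section 9.5 removes from the formal analyses only infants who die within 72 hours; later deaths are simply not replaced. Section 9.6 keeps an infant enrolled at 72 hours in the sample even if it dies soon after.
- Section 9.18.6 asks about mortality at every contact and records the date of death. Section 9.16 collects illness data at sick visits in the first six months. A condition that preceded death may therefore already be on record.
- For the extension, 9.20 uses the full cohort for morbidities over time, and its multilevel models can use incomplete series.
- The direction of bias depends on case fatality, and its size rests on assumed inputs.

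All of this stands, and it rules out calling under-counting a feature of the plan. It does not close the gap. Keeping deaths in the cohort does not say how they enter a percentage. The multilevel models appear in the context of growth and do not produce the percentages in 9.12. Infants lost early remain a problem even if every death is counted.

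It is also fair that section 9.18.6 lists no onset date for each morbidity, and that the illness diaries start only at week 6 as a recall aid. That limits how finely onset can be timed. It does not prevent an estimate by visit interval.

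**Conclusion.** The point holds as an omission with a cheap remedy. For cumulative outcomes at about 14% attrition that includes deaths, a simple proportion can be biased with either denominator, and 9.20 specifies neither. Among those remaining, a condition is under-counted if its case fatality exceeds overall cohort mortality and slightly over-counted otherwise. Over all enrolled, early losses pull the figure down.

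The documents cannot give the size, because the number of deaths and the condition frequencies are assumed throughout. In most of the scenarios examined the bias is smaller than the sampling margin. It exceeds the margin only when deaths make up a good part of the 50 and most of those infants had the condition. Sections 9.5 and 9.12 also give different reasons for the same drop and need to be reconciled.

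**What to change.** In section 9.20:

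- Use all enrolled infants alive at 72 hours as the denominator for every cumulative outcome, in line with the existing 72-hour rule in 9.5, and count conditions recorded before death.
- Report 6- and 12-month cumulative incidence by the Aalen-Johansen method, with death as a competing event, loss and withdrawal (including no re-consent at 6 months) as censoring, and onset assigned to the visit interval. Use Kaplan-Meier for mortality. Keep the planned allowance for clustering of twins.
- Keep simple proportions for status at a point in time, such as stunting at 6 months, labelled as among survivors seen.

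In sections 9.5 and 9.12, give one list of causes for the drop of 50, with deaths counted separately from loss and withdrawal.

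The cost is wording and slightly more analysis work. Date of death (9.18.6) and infant health at each scheduled contact (Tables 7 and 7.1) are already collected, so no extra participants or visits are needed. Two limits remain: onset is known only to the visit interval, which is wider after 6 months, and censoring assumes that infants lost have the same later risk as those still followed.

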9.13 Response rates

The four study sites vary in annual birth volume and rate of LBW births (Table 6). The enrollment period for the prospective cohort will be approximately four months long (see Gantt chart), and each site expects

to have an estimated number of LBW babies born in that period. The table shows the response rates needed in each site in order to enroll 300 women into the cohort.

Table 6: Birth volume and response rates

Site	No. of study facilities	Annual birth volume		4-month study period	
		All births	LBW births (estimated)	LBW births (estimated)	Required response rate ¹
Dar es Salaam	3	35,997	5,550	1,850	16%
Lilongwe	2	20,000	1,280	427	70%
Karnataka	5	21,000	2,100	700	43%
Odisha	2	19,600	3,320	1,107	27%

¹ Percent of LBW births that need to be enrolled in order to achieve a total sample of 300; please note we may have a longer enrollment period than 4 months if required.

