Objectives	1: Understand the current practices and standard of care (SOC) for feeding LBW infants	2: Define and document the key outcomes (including growth, morbidity, and lack of success on MOM) for LBW infants under current practices	3: Assess the acceptability and feasibility of a system-level IYCF intervention and the proposed infant feeding options for LBW infants

To meet the first study objective of understanding practices, routine care and standard of care (SOC) for LBW infant feeding, we will use a mixed methods approach. First, we will conduct focus group discussions (FGD) with clinicians, mothers, family members, and religious leaders to understand current SOC and cultural practices around infant feeding. Second, we will enroll 35 mothers and up to 60 infants per site (approximately 35 pairs) for close in-facility feeding observation before discharge, focusing on the behaviors and interactions between mother, infant, and clinic staff regarding infant feeding. These feeding observations may be conducted in the neonatal care unit and Neonatal Intensive Care Unit (NICU), if applicable. Third, we will enroll and follow a prospective cohort of approximately 300 mothers and their LBW infants at each site. Caregivers of all LBW infants at each site will be approached for consent. All enrolled infants will be followed prospectively for up to six months through a regular schedule of clinic visits, and mothers will be regularly interviewed on their normal feeding practices and related topics. Anthropometric measurements will be taken across the six months of follow up. Fourth, a set of structured facility observations will assess the current patterns of infant feeds and maternal milk in the health facility to understand how infant feeds are currently provided under SOC.

For the 6-month extension:

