9.2 Recruitment of infants born in the facility

All LBW infants will be screened at study facilities to determine their eligibility for the prospective cohort. LWB infants will be identified directly after birth in the same way as for the in-facility observations, and study staff will be notified (described above).

Some of the inclusion/exclusion criteria are best assessed through a brief chart check or discussion with clinicians. Once a LBW birth is identified, study staff will record on the screening instrument:

- Mother's age
- Congenital abnormalities, as defined in I/E criteria
- Infant critical or severe illness, as defined in I/E criteria

If the mother/infant pair is still eligible after these checks, then study staff will approach the woman to check the final criteria, which are whether she plans to leave the study area in the next six months. If she is still eligible, then we will progress to the consent process.

The target time for approaching a woman for the prospective cohort will be between 1 and 6 hours after the birth, but not within the first hour after the birth. There is a maximum time cutoff of 72 hours for recruitment to the prospective cohort; women can be enrolled at any time up to their discharge from the facility or 72 hours (whichever was first).

If an infant is born overnight when no study staff are present, then study staff will review the register or medical records when they arrive for their shift in the morning. Women can be approached for inclusion at that point. To avoid bias, we will pick the odd number admissions to select children for enrollment (1,3,5,7th admissions overnight) for inclusion.

6-month extension: This is not applicable see section 9.4

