Personnel	Hiring, on-boarding, training																																						
Develop data processes	SOPs, data architecture, data quality assurance plan	1			2			3			4																												
Procurement	Assets: tablets, computers, measurement tools	1			2			3																															
Relationship development	Stakeholder buy-in (national and facility level)	1			2			3																															
In-facility observations of LBW infants																																							
Data collection	Target N = 45/site																				1																		
Data analysis																					2																		
Prospective cohort																					3																		
Data collection	Enrollment period, N=300/site	1			2			3			4			5			6			7																			
Data analysis	Follow up period																						8																
Data analysis	6-week outcomes																						9																
Facility Context Assessments																					10																		
Data collection	Administered at end of study at each site																				11																		
Data analysis																					12																		
Qualitative research																					13																		
Data collection	FDGs, IDIs, Translation/Transcription	1			2			3			4			5			6			7																			
Data analysis																					8																		
Desk research: Chart review																					9																		
Data collection	Target n = 155 per site	1			2			3			4			5			6			7																			
Data analysis	6-wk and 6-mo outcomes																				8																		
Desk research: Literature review																					9																		
Initial review		1			2			3			4			5			6			7																			
Main review																					8																		
Propose a Strategy for Testing																					9																		
Synthesis of findings	Analyze data streams together where possible																				10																		
Interpretation of findings	Country-level analysis workshops																				11																		
Design IYCF strategies	Draft IYCF design, write white paper, refine strategies with stakeholders																				12																		

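### Table 6 works out the required response rates for enrolling 300 mothers, but the enrolment target is 350; at Lilongwe the four-month rate for that target is 82%, not 70%

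*Combined protocol and SAP*

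**What the plan says.** Two sections give the enrolment target, and they agree. Section 9.5: "We aim for 350 mothers at enrollment with 300 still" in the study at six months, the difference of 50 being put down to loss to follow-up and deaths. Section 9.12: "we propose aiming for 350 enrolled mothers at each site, with an estimated final sample of 300 mothers in each site". Section 9.12 also judges this target achievable within the study period.

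Section 9.13 then tests feasibility over an enrolment period of about four months. Its lead sentence reads "The table shows the response rates needed in each site in order to enroll 300 women into the cohort", and the Table 6 footnote defines the rate as "Percent of LBW births that need to be enrolled in order to achieve a total sample of 300". The footnote adds that enrolment may last longer than four months if needed. The printed rates are 16% (Dar es Salaam), 70% (Lilongwe), 43% (Karnataka) and 27% (Odisha).

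The number 300 is attached to enrolment in two other places. The section 15 timeline has "Enrollment period, N=300/site", and section 4 has "Third, we will enroll and follow a prospective cohort of approximately 300 mothers and their LBW infants at each site".

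**The concern.** The 300 in Table 6 is the number expected to be left after losses, not the number to recruit. The plan thus carries two enrolment numbers, and its only feasibility figures test the lower one. The statement in section 9.12 that the target is achievable has no figures behind it for 350.

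This matters most where there is least slack. Lilongwe has the fewest LBW births in the window, and its printed 70% is already the highest rate in the table. A team planning from Table 6 would not see that the actual target may need more than four months there. A site that took 300 as its enrolment number and stopped would finish well short of 300 at six months.

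**Working it through.** **Inputs.** From Table 6, annual LBW births are 5,550 (Dar es Salaam), 1,280 (Lilongwe), 2,100 (Karnataka) and 3,320 (Odisha). From sections 9.5 and 9.12, 350 mothers are enrolled and 300 remain, so planned attrition is 50/350 = 14.3%. Inflating for attrition, 300/(1 − 50/350) = 350, so the two numbers fit each other.

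**Formula.** Required rate = mothers to enrol ÷ (annual LBW births × 4/12).

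| Site | LBW births in 4 months | Printed | 300 ÷ births | 350 ÷ births |
|---|---|---|---|---|
| Dar es Salaam | 1,850 | 16% | 16.2% | 18.9% |
| Lilongwe | 426.7 | 70% | 70.3% | 82.0% |
| Karnataka | 700 | 43% | 42.9% | 50.0% |
| Odisha | 1,106.7 | 27% | 27.1% | 31.6% |

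All four printed rates reproduce with 300 as the numerator; none does with 350.

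**Slack for the 350 target.** LBW births not needed for enrolment:
- Lilongwe: 426.7 − 350 = 76.7 (18.0%), against 426.7 − 300 = 126.7 (29.7%) for 300.
- Dar es Salaam: 1,850 − 350 = 1,500.
- Karnataka: 700 − 350 = 350.
- Odisha: 1,106.7 − 350 = 756.7.

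**If the printed rate is all that is achieved.** At Lilongwe, 70% of 427 is about 300 enrolled in four months. At the plan's attrition, 300 × 300/350 ≈ 257 would remain. Reaching 350 at 70% would take 350 ÷ (0.70 × 1,280/12) ≈ 4.7 months.

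**Effect on precision.** For a true proportion of 5%, the 95% margin is 1.96 × √(0.05 × 0.95/n). This gives 2.47 percentage points at n = 300 and 2.66 at n = 257.

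**Limits of the table's basis.**
- *Numerator.* It counts mothers, while the footnote speaks of births. With both twins enrolled at the doubled multiple-birth rates of section 9.12, Lilongwe needs 350 × 1.0416 = 364.6 infants, or 364.6/426.7 = 85.4%, leaving about 62 births.
- *Denominator.* It is all LBW births. It therefore includes infants the cohort cannot take: those under 1500 g, those living outside the catchment area, and half of overnight admissions, because "we will pick the odd number admissions to select children for enrollment". It may also leave out births elsewhere, which section 9.1 makes eligible. The documents size neither effect, so the net direction is unknown.
- *Replacement.* For an enrolled infant who dies within 72 hours, "we will recruit an additional infant in its place", so slightly more than 350 may have to be recruited.

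**Sensitivity at Lilongwe.** Assume the enrollable pool is a fraction f of the tabulated births. The f values are assumptions; the documents supply none.

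| f | 300 ÷ (f × 426.7) | 350 ÷ (f × 426.7) |
|---|---|---|
| 1.1 | 63.9% | 74.6% |
| 1.0 | 70.3% | 82.0% |
| 0.9 | 78.1% | 91.1% |
| 0.8 | 87.9% | 102.5% |

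The break-even for 350 in four months is f = 0.82. Below it the target cannot be met in that window, even with no refusals.

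**The case against.** The best defence is that Table 6 does what it announces. It gives the rate for 300 women, and for that quantity 70% is right. This stands: the fault is in the input, not the division. Reading the footnote's total as the final sample does not help, because the same footnote speaks of births to be enrolled, and 70% of 427 gives 300 enrolled, not 300 retained.

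The second defence is that little follows from it. Section 9.12 does no hypothesis testing on the cohort and requires no particular sample size. The footnote allows a longer enrolment, about 4.7 months at the printed rates (4 × 350/300). Precision barely moves. All of this is true, and it keeps the point from being serious. It does not make 300 the correct enrolment number, and nothing in Table 6 tells the reader that an extension may be needed.

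Third, the section 4 sentence may simply describe the cohort as followed, and the extension text uses about 300 for pairs already followed for six months. That is a fair reading. The conflict rests mainly on section 9.13 and the timeline label.

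Fourth, the extension sections describe pairs already in follow-up, so enrolment was under way when they were written. This reduces the planning value of a restated table but leaves its use as a benchmark.

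**Conclusion.** The concern holds. Table 6 understates the response rate needed for the plan's own enrolment target at every site, by a factor of 350/300 = 1.17. The largest gap is at Lilongwe, where the rate is 82.0% rather than 70%. No section reconciles the two numbers.

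The 82% rests on the table's four-month window and its LBW birth estimates. It counts mothers, not infants, and treats every LBW birth as available. The rate among mothers who can actually be approached could be higher or lower. The other three sites have room on the same basis.

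This is an inconsistency that should be corrected. It does not threaten the validity of the estimates.

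**What to change.** 1. Recompute the last column of Table 6 for 350 enrolled mothers (18.9%, 82.0%, 50.0%, 31.6%), and change the lead sentence and footnote to match.
2. In section 4 and the section 15 timeline, either give 350 as the enrolment number or label 300 as the number expected at six months.
3. Add a short note to Table 6 that the numerator counts mothers (about 85% at Lilongwe if both twins enrol), and that the denominator is all LBW births, which includes infants the cohort cannot enrol and may omit births outside the facilities.
4. Judge from the restated rates whether four months is enough at Lilongwe, using the extension the footnote already permits. If enrolment is complete, use the restated rates as the benchmark when reporting enrolment achieved.

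The cost is one table column, its lead sentence and footnote, one sentence in section 4 and one timeline label. No participants are added, since 350 is already the target; the stated rates simply become less favourable.
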